### 16.1.6. Causality

The relationship of each adverse event must be determined by a medically qualified individual who is on the delegation log for the trial. If any doubt about the causality exists, the local Principal Investigator should inform the Chief Investigator. The following definitions should be used to determine causality:

Unrelated	The event is not considered to be related to enalapril.
Unlikely to be related	The event is considered unlikely to be related to enalapril; there is little evidence to suggest a causal relationship or there is another reasonable explanation for the event.
Possibly related	Although the relationship to enalapril, cannot be ruled out, the nature of the event, the underlying disease, concomitant medications or temporal relationship make other explanations plausible.
Probably related	The temporal relationship and an absence of a more likely explanation suggest that enalapril is the most likely cause.
Definitely related	The known effects of enalapril indicate this to be the most likely cause and other contributing factors can be ruled out.

### 16.1.7. Severity

The severity of each adverse event must be determined by a medically qualified individual who is on the delegation log for the trial. The following definitions should be when determining severity:

Grade 1	Minor adverse event, not requiring medical intervention. May be asymptomatic and is likely to be a clinical or diagnostic observation only; or may be a symptomatic but minor, or transient event, with no necessity for medical intervention. This might include asymptomatic laboratory or radiographic findings. A minor adverse event is likely to have only marginal clinical relevance.
Grade 2	An adverse event which may require some medical intervention (local/non-invasive) and which is symptomatic to patient. May affect activities of daily living.
Grade 3	Significant symptoms reported, requiring medical intervention and possibly requiring hospitalisation. Medically significant and likely to be significantly affecting activities of daily living.
Grade 4	An adverse event that requires urgent intervention or may have life-threatening consequences.
Grade 5	Death related to the adverse event.

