## 7. Introduction

### 7.1. Background

Breast cancer is the most common malignancy among women worldwide, with over 50,000 new UK cases every year. Treatment commonly includes surgery, anthracycline-based chemotherapy and radiotherapy, and is highly effective. However, anthracyclines can cause immediate, irreversible, damage to cardiac cells and, ultimately, impaired cardiac function and heart failure.

Anthracyclines, including epirubicin, are administered in an outpatient setting and are usually well tolerated. However, they have a dose-dependent toxic effect on the heart which can result in heart failure often only evident years after exposure. The long-term incidence is approximately 5%; this may be higher in older patients. Asymptomatic left ventricular systolic dysfunction (LVSD) is more common, evident in 9.7% of patients with breast cancer within 12 months. LVSD affects cardiac prognosis and limits subsequent cancer treatment options, particularly those that target the HER2 pathway such as trastuzumab (Herceptin). Waiting until anthracycline-induced heart failure becomes clinically evident is ill-advised. Response to treatment is poor and survival at 2 years is 40%; considerably worse than other causes of heart failure and for breast cancer itself.

The burden of cardiotoxicity is particularly important in a patient group in whom 78% will be alive 10-years following their cancer diagnosis. Preventing cardiac damage would offer clear benefits to patients and substantial costs savings to the NHS.

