##### **14.6.2. Dose evaluation visit 1**

Two to five days after the start of enalapril, the patient should return for a dose evaluation visit. Blood pressure and U&Es should be measured and the patient should be assessed for side effects.

If the patient has systolic BP  $\geq$ 100 mmHg, normal serum potassium (potassium  $<$ 5.5 mmol/L), and stable renal function (serum creatinine  $<$ 30  $\mu$ mol/L increase from baseline over 48-96 hours) then the enalapril dose should be up-titrated to 5mg BD.

If the patient is, in the clinical opinion of the investigator, unlikely to tolerate a higher dose at this point then the dose should remain the same. At the discretion of the investigator, a further assessment at

dose evaluation visit 2 could be made to consider up-titration of enalapril to 5mg BD using the same criteria as above.

If the patient has a  $\geq 30$   $\mu\text{mol/L}$  increase in serum creatinine levels since the last assessment compared to baseline, new hyperkalaemia (potassium  $\geq 5.5\text{mmol/L}$ ), or symptomatic hypotension (SBP  $< 100\text{mmHg}$ ) then enalapril should be permanently discontinued and the patient withdrawn from the study. The patient should be seen again within 7 days to ensure the reasons for withdrawal have resolved to the satisfaction of the investigator.

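### The severity scale offers no Grade 2 or 3 for an asymptomatic potassium or creatinine result, although the protocol's own enalapril rules act on such results

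*Combined protocol and SAP*

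**What the plan says.** Section 16.1.7 defines five grades. The first four matter here.

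- Grade 1: "Minor adverse event, not requiring medical intervention". Of asymptomatic results it says "This might include asymptomatic laboratory or radiographic findings", and it adds "A minor adverse event is likely to have only marginal clinical relevance", which is worded as a probability and not as a rule.
- Grade 2: "An adverse event which may require some medical intervention (local/non-invasive) and which is symptomatic to patient".
- Grade 3: "Significant symptoms reported, requiring medical intervention and possibly requiring hospitalisation".
- Grade 4: "An adverse event that requires urgent intervention or may have life-threatening consequences".

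The enalapril rules act on laboratory values without asking for symptoms. At dose evaluation visit 1 (14.6.2), a creatinine rise of at least 30 µmol/L or a new potassium of at least 5.5 mmol/L is a trigger, and "then enalapril should be permanently discontinued and the patient withdrawn from the study". Only the hypotension trigger is described as symptomatic. At visits 2 and 3 (14.6.3, 14.6.4) similar laboratory triggers lead to a dose reduction. Section 13.2.9 leaves the response to a creatinine rise to clinical judgement, which may include a temporary or permanent halt. Section 14.6.5 refers to halts for renal instability.

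Section 14.5 lists hyperkalaemia among the very common side effects of enalapril and renal impairment among those it calls common and severe. Quantifying side effects is a secondary objective (8.2). Every adverse event is assessed for severity (16.5), and section 17.1, Statistical Analysis, plans a cross-tabulation of adverse events.

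**The concern.** The scheduled U&E tests exist to find potassium and creatinine changes before the patient feels anything. Two of enalapril's recognised harms will therefore often be asymptomatic when found. A scale that reserves its middle grades for symptomatic events cannot place those harms there, even when the protocol treats the same result as reason to reduce or end trial treatment.

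At stake is the description of harm. A severity table would tend to show these events in a grade described as probably of marginal relevance. Alternatively, it would show them scattered across grades according to how each assessor resolved the gap. Severity is also named as an element of expectedness (16.1.3, 16.1.5), so an unclear grade may carry over into that judgement.

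**Working it through.** There is no figure to reproduce. The check applies the grade definitions to an asymptomatic event and compares the result with the enalapril rules.

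**Step 1. Conditions of each grade (16.1.7).**

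| Grade | Symptoms required? | Intervention |
|---|---|---|
| 1 | No | None needed |
| 2 | Yes (joined by *and*) | May be needed, local or non-invasive |
| 3 | Yes (significant) | Needed |
| 4 | No | Urgent, or consequences may be life-threatening |

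**Step 2. Place an asymptomatic event, by intervention.**

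- (a) No intervention needed: Grade 1.
- (b) Non-urgent intervention needed, not potentially life-threatening: Grade 1 is excluded by its limit on intervention, Grades 2 and 3 by the absence of symptoms, and Grade 4 by the lack of urgency or threat to life. No grade fits.
- (c) Urgent intervention needed, or possibly life-threatening: Grade 4.

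**Step 3. Apply this to the protocol's triggers.** Take, for illustration, a new potassium of 5.8 mmol/L (limit 5.5) or a creatinine rise of 35 µmol/L (limit 30) at visit 1, without symptoms. Either meets the 14.6.2 trigger for permanent discontinuation. Section 16.1.7 does not say whether stopping or reducing the trial drug counts as medical intervention. If it does not, the event is in (a). If it does, the event is in (b). If the assessor considers it potentially life-threatening, it is in (c). On no reading is it Grade 2 or 3. The same reasoning covers dose reductions at visits 2 and 3 and a halt under 13.2.9.

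**Step 4. Compare the arms' opportunity to be detected.** After baseline, both arms have U&Es before cycles 2 to 6 and one month after the last epirubicin dose: 5 + 1 = 6 common time points. The enalapril arm also has up to three dose evaluation visits, giving up to 6 + 3 = 9, plus any rechecks after dose adjustments. A between-arm comparison of laboratory grades over all visits would therefore mix harm with extra testing. This affects how a repaired scale should be used.

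**The case against.** The strongest reply is that the information survives elsewhere. U&E values go into the eCRF (13.2.9). Temporary halts are noted and explained (14.6.5), reasons for missed doses are recorded (14.7), and withdrawals are captured (12.2). Causality has its own five-level scale (16.1.6), adverse reactions to enalapril are a separate secondary outcome (9.3), and the IDMEC reviews all events (16.5). A medically qualified person assigns the grade. Section 17.1 promises only a cross-tabulation and sets no grade cut-off. All of this is correct and limits the consequence. It does not repair the scale: severity must be assessed for every event, and section 17.1 specifies no table of events leading to a treatment change that would offset the grading.

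A reader might go further, in four ways that the documents do not support.

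- *That such events can only be Grade 1, so enalapril must look safer.* Grade 1 excludes events needing intervention, its statement on relevance is qualified as likely, and the second limb of Grade 4 could be applied to some hyperkalaemia. Grade 1 is the probable default because it alone names such findings, so understatement is likely but not certain.
- *That a fall in LVEF is hidden in the same way.* Section 7.1 says "LVSD affects cardiac prognosis and limits subsequent cancer treatment options", so asymptomatic dysfunction is not trivial. But no rule stops enalapril for it, the only post-baseline study scan is 4 weeks after the last epirubicin dose, and enalapril ends at 3 weeks. LVEF is read by a blinded core laboratory and analysed numerically.
- *That the cytopenias in 16.2 belong here.* They are listed as foreseeable from routine care, not as enalapril harms.
- *That every such result stops enalapril.* Outright discontinuation is mandated only at visit 1.

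**Conclusion.** The point holds as a defect in a stated rule. Section 16.1.7 and the enalapril rules in 13.2.9 and 14.6.2 to 14.6.5 are inconsistent for asymptomatic, actionable laboratory results. Such results fall in Grade 1 or in no grade, and occasionally in Grade 4, but never in Grade 2 or 3.

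The effect is confined to the severity description of side effects and adverse events, with possible carry-over to expectedness. The primary analysis of troponin T is untouched, and SAE status rests on the separate criteria in 16.1.4. The size in patients cannot be calculated: the documents give no expected rate of asymptomatic hyperkalaemia or creatinine rise in either arm, and no table of Grade 2 or higher laboratory events is specified against which a loss could be measured.

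The conclusion that harm would probably be understated rests on one assumption, that most assessors faced with the gap will choose the only grade that mentions such findings. If they do not, the result is inconsistent grading between assessors and sites, which is also a fault. The change is worth making because it is cheap and serves a declared secondary objective.

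**What to change.** 1. In 16.1.7, remove symptoms as a necessary condition of Grades 2 and 3. Grade asymptomatic laboratory abnormalities by measured value, with separate, non-overlapping bands for each grade so that one result cannot satisfy two grades. The trial team should set the bands and reconcile the table with 13.2.9 and 14.6.2 to 14.6.5. No dose or stopping rule is to be altered.
2. Apply the bands identically in both arms. Do not grade by whether enalapril was changed: only one arm has enalapril to change, so that would build a difference between arms into the scale.
3. In the adverse event tabulation, report events leading to reduction, halt or stop of enalapril descriptively, for the enalapril arm only.
4. When comparing arms on laboratory grades, use only the visits common to both (before cycles 2 to 6 and one month after the last epirubicin dose).

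The cost is rewording one table, agreeing the bands and adding one descriptive row. U&E values are already in the eCRF, so any event graded under the present wording can be regraded from recorded data. The downside is that some events will move to a higher grade.

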## 16.2. Foreseeable Adverse Events

Foreseeable adverse events are those which are foreseen in the patient population and as a result of the routine care of patients. If a foreseeable adverse event occurs, and this also fulfils the criteria for an SAE it will not need an SAE report to be submitted for this trial, but will need recording on the CRF as an adverse event. These will not be considered as SUSARs unless the severity of the event was considered to be unexpected.

Foreseeable adverse events are:

- Infection
- Anaemia
- Thrombocytopenia
- Neutropenia
- Nausea
- Vomiting
- Fatigue
- Alopecia
- Diarrhoea
- Stomatitis
- Loss of appetite
- Palmar-plantar syndrome
- Taste changes
- Bladder irritation
- Headache
- Skin changes
- Thrombosis
- Sepsis
- Neutropenic sepsis

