#### **14.5. Known side effects**

Very common side effects related to treatment with enalapril include: cough, dizziness, nausea, asthenia, blurred vision, and hyperkalaemia. Common and severe side effects include angioedema and renal impairment. More detailed information relating to the side effects of enalapril can be found in the SmPC for the product. See Appendix 1.

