#### 16.1.5. Suspected, Unexpected Serious Adverse Reaction (SUSAR)

A serious adverse reaction, the nature and severity of which is not consistent with the information about the IMP in question set out in the RSI.

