## 16.5. Adverse Event Reporting

All AEs will be recorded in the patients' medical notes and on electronic case report forms. AEs will be recorded from the day of randomisation until the last visit or until withdrawal, with the exception of adverse events considered related to enalapril, which will be followed until resolution, a stable outcome or death.

All AEs will be assessed for severity, causality, and seriousness and expectedness by an Investigator. All events will be reviewed by the Independent Data Monitoring and Ethics Committee (IDMEC) as part of their ongoing assessment of safety.

Patients should be asked about any adverse events at each visit.

Where an AE fulfils the criteria for a reportable SAE as part of this trial, this will be reported immediately to NCTU (within 24 hours of the research team becoming aware of the event) who will inform the Sponsor and Chief Investigator. Should the SAE form be incomplete at the time of the initial report, follow-up information should be provided as it becomes available. The relationship to the IMP should be assessed by the Investigator at the site, and they will also assess expectedness in relation to the approved RSI.

Exceptions for SAE reporting include hospitalisation for:

- Routine treatment or monitoring of the studied indication not associated with any deterioration in condition
- Treatment which was elective or pre-planned, for a pre-existing condition not associated with any deterioration in condition
- Any admission to hospital or other institution for general care where there was no deterioration in condition

In the event that a SUSAR is fatal or life-threatening, the sponsor will inform the MHRA and the REC within 7 days. In the event that a SUSAR is non-life-threatening, the sponsor will inform the MHRA and the REC within 15 days.

All Principal Investigators will be informed of all SUSARs throughout the trial, as they occur.

SAEs and SUSARs should be reported to NCTU within 24 hours

[[contact]](mailto:[contact])

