#### **16.6. Foreseeable Adverse Event Reporting**

Foreseeable adverse events should be recorded as adverse events within the trial CRF, but do not require reporting as Serious Adverse Events for this trial.

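### Sections 16.2 and 16.6 waive the SAE report for 19 listed events whatever their causality, and the severity-only SUSAR rule in 16.2 conflicts with 16.1.5 and 16.5

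*Combined protocol and SAP*

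**What the plan says.** Protocol section 16.2 defines its list by the setting and not by the trial drug: "Foreseeable adverse events are those which are foreseen in the patient population and as a result of the routine care of patients". The list has 19 terms, from alopecia and taste changes to thrombosis, sepsis and neutropenic sepsis. For a listed event that is also serious, "it will not need an SAE report to be submitted for this trial, but will need recording on the CRF as an adverse event". The next sentence adds: "These will not be considered as SUSARs unless the severity of the event was considered to be unexpected". Section 16.6 restates the waiver: listed events are recorded in the CRF but "do not require reporting as Serious Adverse Events for this trial".

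Other sections set the general rules:

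- Section 16.1.2 makes any adverse event with a causal relationship to enalapril an adverse reaction, and 16.1.4 makes it a serious adverse reaction if a seriousness criterion is met. Neither excepts listed events.
- Section 16.1.5 defines a SUSAR as a serious adverse reaction "the nature and severity of which is not consistent with the information about the IMP in question", as set out in the RSI.
- Section 16.5 has the investigator assess every adverse event for severity, causality, seriousness and expectedness. A reportable SAE goes to the trials unit (NCTU) within 24 hours, and NCTU informs the Sponsor and Chief Investigator. For these reports the site assesses relatedness, and "they will also assess expectedness in relation to the approved RSI".
- Section 16.7 has deaths attributed to the trial drug reported to the Sponsor at once.

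**The concern.** A list of events expected from the disease and its routine care is a sensible filter for events that nobody attributes to the trial drug. Here the filter also applies when the investigator does attribute the event to enalapril. The waiver then removes the expedited report for a suspected serious reaction to the drug under test.

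The SUSAR sentence adds a second problem. Whether a suspected reaction is unexpected should depend on what is known about the drug. Section 16.2 substitutes a test on severity alone and names no reference against which severity is judged. A site faced with a listed, related, serious event is given two rules that can lead to different actions.

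At stake is the speed at which NCTU, the Sponsor and the Chief Investigator learn of suspected serious reactions in these categories, and whether the 7-day and 15-day notices to the MHRA and the ethics committee in 16.5 are triggered when 16.1.5 says they should be.

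**Working it through.** The plan states no figure on this point and no calculation applies. The check is a comparison of the sections.

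**Step 1: is there a causality condition?** Sections 16.2 and 16.6 are the only places that state the waiver. The trigger in 16.2 is that the event is on the list and meets the SAE criteria; in 16.6 it is that the event is foreseeable. Neither refers to relatedness, and the definition of the list does not supply it.

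**Step 2: can a listed event be related to enalapril?** The protocol's own text shows that it can. Section 14.5 states: "Very common side effects related to treatment with enalapril include: cough, dizziness, nausea, asthenia, blurred vision, and hyperkalaemia". Nausea is also one of the 19 listed terms. Section 16.1.6 has causality graded for each adverse event without excepting listed ones.

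**Step 3: what does the waiver remove?** The 24-hour report and the explicit RSI check in 16.5 are written for a reportable SAE. Sections 16.2 and 16.6 take listed events out of that category.

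**Step 4: follow a listed, serious event judged related to enalapril through the rules.**

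| Case | Under 16.1.5 and 16.5 | Under 16.2 and 16.6 |
|---|---|---|
| (a) Severity judged unexpected | SUSAR if not consistent with the RSI; NCTU within 24 hours | Can be a SUSAR; NCTU within 24 hours |
| (b) Nature not in the RSI, severity unremarkable | SUSAR on nature | Ruled out as a SUSAR; CRF entry only |
| (c) Nature and severity both expected | Serious adverse reaction; SAE report within 24 hours if the waiver did not apply | CRF entry only |
| (d) Death judged caused by the drug | SAE; also immediate report to the Sponsor under 16.7 | No SAE report needed, in tension with 16.7 |

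Case (a) shows no conflict over the route, although 16.2 does not say against what the severity is judged. Case (b) is a direct contradiction between 16.1.5 and 16.2. Case (c) follows from the missing causality condition. Case (d) leaves 16.7 and the waiver unreconciled.

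**Step 5: what still operates?** Listed events are entered on the CRF, and section 20.3 makes NCTU responsible for the trial database, so the data reach NCTU, but with no expedited timeline stated. Under 16.5 the IDMEC reviews all events, and 20.6 has it meet every 6 months. These routes keep the information but do not replace an expedited report.

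**The case against.** The strongest reply is that several safeguards remain, and that a reader could easily infer more than the text supports. Four stronger readings fail.

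- *That such events are never sent to NCTU or never tested as SUSARs.* Section 16.2 keeps the unexpected-severity route, 16.5 has expectedness assessed for all adverse events, 16.7 covers deaths caused by the drug, and CRF entries go to the database that NCTU runs.
- *That sites are told not to report.* The wording of 16.2 and 16.6 waives a report and does not forbid one.
- *That the secondary objective of quantifying enalapril side effects (8.2) is damaged.* Listed events stay in the adverse event data, with seriousness and causality assessed, and the Statistical Analysis section cross-tabulates adverse events. Only the expedited report is lost.
- *That independent review slips from 24 hours to about 6 months.* The 24-hour report goes to NCTU, the Sponsor and the Chief Investigator, who are trial parties. No faster IDMEC route for reported SAEs is described, so the documents show no change in time to IDMEC review.

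Two further points limit the size of the finding. The nausea overlap does not itself show a missed SUSAR: nausea is a known enalapril effect, so its nature is expected and the severity route is the one that matters. The RSI is also not in the documents, so no listed term can be shown to be unexpected in nature. It would be inference, too, to call the list a chemotherapy list; the protocol ties it to the patient population and routine care.

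All of this stands. It does not supply the missing causality condition, and it does not remove the contradiction in case (b).

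**Conclusion.** The point holds as a conflict between stated rules on expedited safety reporting. For 19 event terms, a serious event judged related to any of the 85 planned enalapril patients' trial drug needs no 24-hour SAE report unless its severity is judged unexpected, or it is a death that falls under 16.7. A related serious event whose nature lies outside the RSI but whose severity is unremarkable is a SUSAR under 16.1.5 and is excluded by 16.2.

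The conclusion rests on the text alone and assumes that sites take the waiver at its word. The number of events affected cannot be given, because the documents contain neither event rates nor the RSI. The effect is on the speed and route of reporting, not on whether the events are recorded or analysed.

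**What to change.** Amend the protocol as follows:

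1. In 16.2 and 16.6, limit the waiver to listed events that the investigator assesses as unrelated or unlikely to be related to enalapril, using the categories in 16.1.6.
2. State that a listed event that is serious and assessed as possibly, probably or definitely related is reported under 16.5 within 24 hours.
3. Delete the severity-only SUSAR sentence from 16.2, so that expectedness is judged against the RSI as 16.1.5 and 16.5 already require.
4. Reconcile 16.7 with these sections, so that it is clear how a fatal listed event is reported.

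No new assessment is needed, since 16.5 already calls for causality on every adverse event. The cost is a short amendment and some extra SAE forms. Their number is unknown and may not be small, because the possibly-related category in 16.1.6 is broad: it covers events where a link cannot be ruled out even though other explanations are plausible.
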